8 STUDY POPULATION

Male and female patients ≥ 18 years of age with a histological or cytological diagnosis of renal cell carcinoma, with the presence of oligometastases (1-5 metastases). One or more lesions must be deemed suitable for treatment with SABR. For patients with metastases involving the spine, lesions will be highly selected so they do not pose a significant risk for spinal canal impingement or spinal cord compression.

8.1 Patient Registration

Recruitment will cover a 2-year period. Screening for individual participants will take place within 35 days prior to registration onto the study.

The Investigator should ensure that all requirements are met prior to registering eligible patients on the trial:

- Patient meets all inclusion and exclusion criteria requirements
- Patient has signed and dated all consent forms
- All screening assessments have been completed and recorded in the patient's medical records complete with all relevant source documents

Sites will register eligible patients electronically using the online RAPPORT electronic data capture (EDC) system. Confirmation of registration will also be provided electronically (via email) as well as, a unique 6-digit patient identification number for the patient.

Full training on the RAPPORT EDC system will be provided to sites prior to site activation.

8.2 Replacement of Non-Evaluable Patients

Evaluable patients are defined as participants who complete at least one SABR treatment and receive at least one dose of study drug (18-20Gy/1# to at least one lesion with at least one dose of pembrolizumab).

If a patient receives no treatment (SABR or pembrolizumab) or completes 1 x SABR treatment but does not receive any pembrolizumab treatment (i.e. withdraws or is withdrawn from the study before receiving any study drug), that patient is deemed as 'non-evaluable. Accrual will continue until 30 evaluable patients are obtained.

8.3 Participant Inclusion Criteria

In order to be eligible for participation in this trial, the participant must:

1. Has provided written informed consent for the trial.
2. Be ≥ 18 years of age on day of signing informed consent.
3. Have oligometastases (1-5 metastases), and measurable disease based on RECIST 1.1.
4. Participants must have a histologically or cytologically confirmed metastatic renal cell carcinoma. Oligometastatic lesions do not need to be biopsied but they must be clinically consistent to represent metastatic disease.

5. Patient can either be treatment naïve or have previously received up to 2 lines of systemic treatment (eg. Pazopanib or Sunitinib). If patient has received prior systemic therapy, the total number of metastases that have not been treated with definitive local therapies should not number more than 5.
6. Must have had surgical consideration for metastasectomy and thought appropriate for SABR due to medical inoperability, technical factors or patient declining surgery.
7. Must have at least one metastasis for which SABR is technically deliverable.
8. Be willing to provide archival tissue from a previously biopsied or excised primary or metastatic RCC lesion (if available). If safe to do so, a request for newly obtained specimen (obtained up to 5 weeks prior to trial registration) will be made, however participation for this biopsy is entirely optional.
9. Have a performance status of 0-2 on the ECOG Performance Scale (Appendix 1)
10. Demonstrate adequate organ function as defined in Table 3, all screening labs should be performed within 10 days of registration.

Table 3: Adequate Organ Function Laboratory Values

System	Laboratory Value
Haematological	
Absolute neutrophil count (ANC)	$\geq 1.5 \times 10^9/L$
Platelets	$\geq 100 \times 10^9/L$
Haemoglobin	$\geq 90 \text{ g/L}$ or $\geq 5.6 \text{ mmol/L}$ without transfusion or EPO dependency (within 7 days of assessment)
Renal	
Serum creatinine OR Measured or calculated ^a creatinine clearance (GFR can also be used in place of creatinine or CrCl)	$\leq 1.5 \times$ upper limit of normal (ULN) OR $\geq 30 \text{ mL/min}$ for participant with creatinine levels $> 1.5 \times$ institutional ULN
Hepatic	
Serum total bilirubin	$\leq 1.5 \times$ ULN OR Direct bilirubin \leq ULN for participants with total bilirubin levels $> 1.5 \times$ ULN
AST (SGOT) and ALT (SGPT)	$\leq 2.5 \times$ ULN OR $\leq 5 \times$ ULN for participants with liver metastases
Albumin	$\geq 2.5 \text{ mg/dL}$
Coagulation	
International Normalized Ratio (INR) or Prothrombin Time (PT)	$\leq 1.5 \times$ ULN unless participant is receiving anticoagulant therapy as long as PT or PTT is within therapeutic range of intended use of anticoagulants
Activated Partial Thromboplastin Time (aPTT)	$\leq 1.5 \times$ ULN unless participant is receiving anticoagulant therapy as long as PT or PTT is within therapeutic range of intended use of anticoagulants
^a Creatinine clearance should be calculated per institutional standard.	

11. Life expectancy > 12 months.
12. Be willing and able to comply with all study requirements, including treatment, attending assessments and follow-up.
13. Female participant of childbearing potential should have a negative urine or serum pregnancy within 7 days prior trial registration. If the urine test is positive or cannot be confirmed as negative, a serum pregnancy test will be required.
14. Female participants of childbearing potential should be willing to use 2 methods of birth control or be surgically sterile, or abstain from heterosexual activity for the course of the study through 120 days after the last dose of study medication (see Section 9.4.2: Contraception). Participants of childbearing potential are those who have not been surgically sterilized or have not been free from menses for > 1 year.
15. Male participants should agree to use an adequate method of contraception starting with the first dose of study therapy through 120 days after the last dose of study therapy.

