Whole Blood Sample ^{15,16}		X	X	X		X (9, 12 and 24 months)	X

Clinical/Administrative Assessments

- Vital signs include blood pressure, heart rate, respiratory rate and temperature. Height will be measured at screening only.
- Baseline abnormalities (using CTCAE v4.03) must be recorded from signature of informed consent to prior to start of treatment. Adverse events (using CTCAE v4.03) are then required to be assessed on day 1 of every pembrolizumab cycle and at 30 days following last pembrolizumab treatment. SABR related adverse events will be collected at every subsequent follow-up visit until 2 years after completion of SABR.

3. Conventional hypofractionated radiotherapy of **30-36Gy** may be delivered to individual lesion(s) if SABR is determined to be not technically or safely possible to deliver. If CRT is required it must be completed prior to SABR administration. **At least one lesion must receive SABR.**

4. Pembrolizumab should be administered at 5 days (+/- 3 days) of the last SABR treatment for a total of 8 cycles.

Laboratory Procedures/Assessments – All diagnostic laboratory tests should be performed within 10 days of study registration (to determine eligibility), and also within 3 days prior to every cycle of pembrolizumab (unless indicated otherwise below)

5. Urine or serum pregnancy test for patient of childbearing potential should be performed within 7 days of study registration and also 72 hours within first dose of pembrolizumab. If the urine test is positive or cannot be confirmed as negative, a serum pregnancy test will be required.

6. Haematology: Haematocrit, haemoglobin, platelet count, white blood cell count (total and differential), red blood cell count, absolute neutrophil count and absolute lymphocyte count.

7. Chemistry: Carbon dioxide (if considered standard of care only), uric acid, calcium chloride, glucose, phosphorus, potassium, sodium, magnesium, total protein.

8. Liver Function Tests: Albumin, Alkaline Phosphatase (ALP), Alanine Aminotransferase (ALT), Aspartate Aminotransferase (AST), Lactate Dehydrogenase (LDH), Gamma-Glutamyl Transferase (GGT, total bilirubin and direct bilirubin if total bilirubin is elevated above the ULN), Kidney Function Tests: Urea, creatinine.

9. Thyroid Function: T3, T4 and TSH.

10. Coagulation Profile: PT (INR), aPTT. These need only be done if there is clinical concern regarding patient anticoagulation.

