10.6 Second Course Phase (Pembrolizumab Retreatment Period)

Participants who stop pembrolizumab with SD or better response who then experience radiographic disease progression may be eligible for up to one year of additional treatment with pembrolizumab via the Second Course Phase at the discretion of the investigator if:

- no cancer treatment was administered since the last dose of pembrolizumab,
- the participant meets the safety parameters listed in the Inclusion/Exclusion criteria below, and
- the trial is open.

Participants will resume therapy at the same dose and schedule at the time of initial discontinuation. This retreatment is termed the Second Course Phase of this study and is only available if the study remains open and the participant meets the following conditions:

EITHER

- Stopped initial treatment with pembrolizumab after attaining an investigator-determined confirmed CR according to RECIST 1.1, and
- Was treated for at least 24 weeks with pembrolizumab before discontinuing therapy
- Received at least two cycles of pembrolizumab beyond the date when the initial CR was declared

OR

- Had SD, PR or CR and stopped pembrolizumab treatment for reasons other than disease progression or intolerability

AND

- Experienced an investigator-determined confirmed radiographic disease progression after stopping their initial treatment with pembrolizumab
- Did not receive any anti-cancer treatment since the last dose of pembrolizumab

10.6.1 Has a performance status of 0 or 1 on the ECOG Performance Scale

- Demonstrates adequate organ function as detailed in Section 8.3.
- Female participant of childbearing potential should have a negative serum or urine pregnancy test within 72 hours prior to receiving retreatment with study medication.
- Female participant of childbearing potential should be willing to use 2 methods of birth control or be surgically sterile, or abstain from heterosexual activity for the course of the study through 120 days after the last dose of study medication (Section 9.4.2 Contraception). Participants of child bearing potential are those who have not been surgically sterilized or have been free from menses for > 1 year.
- Male participant should agree to use an adequate method of contraception starting with the first dose of study therapy through 120 days after the last dose of study therapy.

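### The albumin limit in Table 3 is written as 2.5 mg/dL (0.025 g/L), so the albumin row as written excludes nobody, at entry or for the Second Course

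*Combined protocol and SAP*

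**What the plan says.** Inclusion criterion 10 in Section 8.3 requires that the participant "Demonstrate adequate organ function as defined in Table 3, all screening labs should be performed within 10 days of registration". Under its hepatic heading, Table 3 carries the row "Albumin $\geq 2.5 \text{ mg/dL".

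This is the only albumin limit in the documents. The notes to the Schedule of Events (Section 2) name albumin as a test to be done, "Liver Function Tests: Albumin, Alkaline Phosphatase (ALP", but give no limit or unit there.

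The limit is used twice. Section 10.6, which governs re-entry to pembrolizumab for up to one further year, includes the condition "Demonstrates adequate organ function as detailed in Section 8.3".

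The haemoglobin row of the same table is stated in two units: "\geq 90 \text{ g/L}$ or $\geq 5.6 \text{ mmol/L}$ without transfusion or EPO dependency".

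**The concern.** An eligibility limit has to lie within the range that patients can show, or it does nothing. A serum albumin threshold in single milligrams per decilitre is far below any value a laboratory would report for a living patient, so the unit, and perhaps the number, cannot be what was intended.

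Safety is the primary objective, and the table defines which patients are fit enough to enter. Section 8.1 has the investigator confirm every criterion before registration. Section 13.3 requires the trial to be run as the approved protocol describes, with any deviation recorded and explained. A site that follows the text therefore applies no albumin limit. A site that substitutes its own reading applies a limit the protocol does not contain. The same holds for the retreatment decision.

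**Working it through.** **Inputs**

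- Written albumin limit: 2.5 mg/dL (Section 8.3, Table 3).
- Haemoglobin limit in the same table: 90 g/L or 5.6 mmol/L.
- Serum albumin in patients: not in the documents. Assumed range 5 to 50 g/L, chosen to run from extreme hypoalbuminaemia to high normal.
- Haemoglobin monomer mass: not in the documents. Assumed 16.114 g/mmol, used only for a unit check.

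**Step 1. Convert the written limit.**

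2.5 mg/dL × 10 dL/L = 25 mg/L, and 25 mg/L ÷ 1,000 mg/g = 0.025 g/L.

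**Step 2. Compare it with values a patient could have.** The ratio is assumed albumin ÷ 0.025 g/L.

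| Assumed albumin (g/L) | Same value (mg/dL) | Ratio to written limit | Passes |
|---|---|---|---|
| 5 | 500 | 200 | yes |
| 10 | 1,000 | 400 | yes |
| 20 | 2,000 | 800 | yes |
| 30 | 3,000 | 1,200 | yes |
| 50 | 5,000 | 2,000 | yes |

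The smallest margin is 200-fold, at the lowest assumed value. To fail the row, a patient would need albumin below 0.025 g/L.

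**Step 3. Check whether the table's units are unreliable in general.** For haemoglobin, 90 g/L ÷ 16.114 g/mmol = 5.59 mmol/L, which agrees with the stated 5.6. In reverse, 5.6 × 16.114 = 90.2 g/L. The units in that row are coherent. Albumin is the only Table 3 limit expressed per decilitre. The blood counts and haemoglobin are per litre, and the remaining rows use multiples of the upper limit of normal or mL/min.

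**Step 4. Look for a correction elsewhere.** The Schedule of Events gives no unit or limit for albumin, and Section 10.6 only points back to Section 8.3. Nothing in the documents supplies another figure.

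**Step 5. Trace what depends on the cell.** Criterion 10 and the Section 10.6 condition depend on it. The sample size of 30, the Table 8 intervals (Section 11.2.9) and the early termination criteria (Section 11.2.10) do not use it.

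**The case against.** The strongest reply is that this is a unit slip in one cell with little practical effect.

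- **The other limits still operate.** Table 3 keeps working limits for neutrophils, platelets, haemoglobin, creatinine or clearance, bilirubin, AST/ALT, INR/PT and aPTT. A reader might infer that the organ-function criterion as a whole is empty. The table does not support that: only the albumin row fails.
- **There are backstops.** Exclusion 15 in Section 8.4 lets the investigator exclude for a laboratory abnormality, and the closing condition of Section 10.6 repeats this for retreatment. Entry also requires life expectancy above 12 months and ECOG 0-2, and retreatment requires ECOG 0 or 1. A severely hypoalbuminaemic patient is therefore not automatically admitted. This stands, but the laboratory-abnormality clauses rest on judgement and the other two criteria do not test albumin. None of them is a numerical albumin threshold.
- **Sites would probably notice.** The limit is so implausible that a clinician comparing it with a laboratory report may well query it. A reader might infer that sites will diverge and that the safety population will depend on which site registers the patient. Divergence is possible, but nothing in the documents shows that it occurs or is likely, and they do not give the number of sites.
- **The text was read from a PDF.** A transcription error cannot be ruled out from the text alone. This carries little weight: the cell has its operator, number and unit, and neighbouring units came through intact.

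These points limit the consequence. None of them makes the albumin row work.

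**Conclusion.** The point holds for the albumin row. As written, the limit is 0.025 g/L and excludes nobody, at entry or for the Second Course. The conclusion rests on the assumed range of 5 to 50 g/L, but with a margin of at least 200-fold it is not sensitive to that choice.

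The effect on the trial's results cannot be sized. The documents give no albumin distribution, so the number of patients between the written and the intended limit is unknown and may be zero. Two figures might tempt a reader to go further:

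- One patient in 30 is 3.3 percentage points of the grade 3 or higher proportion (1/30). That is true of any patient with such an event, however admitted, and the documents show no link between albumin and toxicity. It does not measure this error.
- Against an assumed lower normal limit of 35 g/L, the written limit is 1,400 times too low (35 ÷ 0.025). The documents contain no such normal limit and do not suggest it was the intended threshold, so the ratio does not give the size of the unit error.

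This is a binding eligibility threshold that is wrong as written. It is worth correcting, and it has no bearing on the planned analyses.

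**What to change.** The sponsor should confirm the intended albumin value and unit and correct the Table 3 cell. Stating the limit in g/L would match the haemoglobin row. This review does not propose the value. Section 10.6 needs no separate edit, because its reference to Section 8.3 carries the correction across. Any registration checklist or data-capture check that repeats the limit should be aligned with it.

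The cost is one table cell in the next amendment. No new test is needed: albumin is already among the scheduled laboratory tests at screening and on day 1 of each pembrolizumab cycle.

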8.4 Participant Exclusion Criteria

The participant must be excluded from participating in the trial if the participant:

1. Based on clinician assessment of disease volume and rate of progression of patient's tumour deposits, the patient requires immediate TKI therapy.
2. Has had previous high dose radiotherapy (biological equivalent of >30Gy in 10#) to an area to be treated which includes vertebral bodies (see below).
Note: Previous high dose radiotherapy is defined as a biological equivalent dose to above that of 30 Gy in 10 fractions using an α/β ratio [82] of 3. Where a patient has received radiotherapy to an equivalent or lower dose than defined above, stereotactic radiotherapy of the area may be considered. In doing so, assessment of the volume and total dose received by any overlap region must be made, and documented by generating a cumulative plan incorporating both the previous and current treatment fields. It is the treating radiation oncologist's responsibility to review both the current plan and the cumulative plan inclusive of previous radiotherapy.
3. Has evidence of untreated or active intracranial metastases. Patients who have had fully resected brain metastasis or those controlled by stereotactic radiotherapy are eligible as long as they are not requiring corticosteroids for symptomatic control.
4. Has evidence of Spinal Cord Compression.
5. Has a Spinal Instability Neoplastic Score ≥ 7 unless lesion reviewed by a neurosurgical service and considered stable (see Appendix 3).
6. Requires surgical fixation of bone lesion for stability. This must be performed before enrolment into the trial.
7. Has a known history of active TB (Bacillus Tuberculosis).
8. Hypersensitivity to pembrolizumab or any of its excipients.

9. Has had a prior anti-cancer monoclonal antibody (mAb) within 4 weeks of registration or who has not recovered (i.e., \leq Grade 1 or at baseline) from adverse events due to agents administered more than 4 weeks earlier.
10. Has had prior chemotherapy, targeted small molecule therapy, or radiation therapy within 2 weeks of registration or who has not recovered (i.e., \leq Grade 1 or at baseline) from adverse events due to a previously administered agent.
Note: Participants with \leq Grade 2 neuropathy are an exception to this criterion and may qualify for the study.
Note: If participant received major surgery, they must have recovered adequately from the toxicity and/or complications from the intervention prior to starting therapy.
11. Has a known additional malignancy that is progressing or requires active treatment. Exceptions include basal cell carcinoma of the skin or squamous cell carcinoma of the skin that has undergone potentially curative therapy or in situ cervical cancer.
12. Has active autoimmune disease that has required systemic treatment in the past 2 years (i.e. with use of disease modifying agents, corticosteroids or immunosuppressive drugs). Replacement therapy (e.g. thyroxine, insulin, or physiologic corticosteroid replacement therapy for adrenal or pituitary insufficiency, etc.) is not considered a form of systemic treatment.
13. Has a history of (non-infectious) pneumonitis that required steroids or current pneumonitis.
14. Has an active infection requiring systemic therapy.
15. Has a history or current evidence of any condition, therapy, or laboratory abnormality that might confound the results of the trial, interfere with the participant's participation for the full duration of the trial, or is not in the best interest of the participant to participate, in the opinion of the treating investigator.
16. Has known psychiatric or substance abuse disorders that would interfere with cooperation with the requirements of the trial.
17. Is pregnant or breastfeeding, or expecting to conceive or father children within the projected duration of the trial, starting with the screening visit through 120 days after the last dose of trial treatment.
18. Has received prior therapy with an anti-PD-1, anti-PD-L1, or anti-PD-L2 agent.
19. Has a known history of Human Immunodeficiency Virus (HIV) (HIV 1/2 antibodies).
20. Has known active Hepatitis B (e.g., HBsAg reactive) or Hepatitis C (e.g., HCV RNA [qualitative] is detected).
21. Has received a live vaccine within 30 days of registration.

9 TRIAL TREATMENTS

The treatment regimen involves the delivery of a single fraction of highly conformal SABR delivered with either photons, electrons or mixed modalities. No cytotoxic chemotherapy is allowed within 3 weeks either side of, or concurrently with respect to the investigational treatment. Consultation with both the treating radiation oncologist and medical oncologist is strongly recommended if chemotherapy is to be considered after the investigational treatment and before documented disease progression, to prevent unforeseen combined toxicities. The first dose of pembrolizumab will be delivered at 5 days (+/- 3 days) after the last SABR treatment for a total of 8 cycles.

9.1 Megavoltage Radiotherapy

The investigational treatment will be prescribed to the covering isodose, ensuring that 99% of the PTV is covered by 100% of the dose (D99=100%). However, a target coverage of D95=100% is acceptable if required to respect an organ-at-risk dose tolerance. Intensity Modulated Radiation Therapy (IMRT) is not compulsory but will be considered if very steep dose gradients have to be achieved or targets 'wrap around' a critical structure. This is the near minimum dose to the target as considered by the International Commission of Radiation Units and Measurements (ICRU) in their report 83 [83]. Multi-field photon treatment, intensity modulated radiation therapy (IMRT), dynamic conformal arcs, electrons and volumetric modulated arc therapies (VMAT) can all be considered.

A single fraction of SABR approach will be utilized, which is the most commonly used dose/fractionation schedule utilized at the Peter MacCallum Cancer Centre. The dose will be prescribed using a 'stereotactic' paradigm to an isodose line no less than 70% of the maximum dose, aiming for a prescription isodose of 80%. This allows for larger target dose inhomogeneities but results in a steeper dose fall off outside of the target volume.

If more than one lesion is to be treated in a single patient, treatment of all lesions ideally would be given in one setting for patient convenience. However for practical or logistic reasons this may not always be possible and in such cases all lesions should be treated within a time window spanning not more than 21 calendar days. Dose for each lesion will be independently verified before treatment and image guidance will be used to ensure accurate patient positioning.

